12.6.2 Per Protocol Set (PPS)

Efficacy will be assessed in the population of PPS comprised of subjects of FAS who meet all the following criteria. PPS is the primary efficacy analysis set.

- Subjects who meet all of the inclusion criteria and none of the exclusion criteria;
- Subjects who have received ≥ 6 times of the specified dose (dose interruption according to the dose discontinuation criteria (section 6.1.3) will be considered as

being dosed but dose interruption due to SAE will not be considered as being dosed) in the initial dose evaluation period; and

- Subjects with no major violations of the study protocol in the initial dose evaluation period.

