6.1.1 Initial-dose evaluation period (Week 1 to Week 8)

AMG531 will be administered at a dose of 1, 3, 6, or 10 µg/kg SC QW for 8 weeks. Dose adjustment (either escalation or reduction) will not be allowed during the initial dose evaluation period except for the cases defined in the 6.1.4 Criteria for discontinuing and resuming study treatment.

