6.1.3 Long-term treatment period (Week 53 to Week156)

6.1.3.1 Initial Dose

AMG531 will be administered SC QW at the same dose received as the last dose in the extension period. If dose adjustment is deemed to be necessary at Week 53 by investigator,

the dose may be adjusted according to the Table 6.1.3-1 Dose adjustment (long-term treatment period) table.

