6.1.4 Criteria for discontinuing and resuming study treatment

If the platelet has exceeded $400 \times 10^9/L$ during the treatment period, study treatment will be temporarily discontinued. Once the platelet count falls to $< 200 \times 10^9/L$, administration of AMG531 will resume at a reduced dose by one level according to the protocol. Once the platelet count falls to $\leq 50 \times 10^9/L$ during the treatment with reduced dose by one level, dosing will be resumed at the temporarily discontinued dose.

If the platelet has exceeded $200 \times 10^9/L$ during the treatment period, the dose of AMG531 will be reduced to the next lower dose tested. If the temporarily discontinued dose is $1 \mu\text{g/kg}$, treatment will be resumed at the dose of $1 \mu\text{g/kg}$.

Other than the reasons above, investigator can reduce the dose at any time during the study if safety concerns arise.

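### Section 12.6.2 cites the wrong section for credited interruptions and does not credit the dose reductions that 6.1.4 requires, so early strong responders can be excluded from the primary analysis set

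*Combined protocol and SAP*

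**What the plan says.** Section 12.6.2 makes the PPS the primary efficacy set. One entry condition is "Subjects who have received ≥ 6 times of the specified dose (dose interruption according to the dose discontinuation criteria (section 6.1.3"). Those interruptions count as "being dosed but dose interruption due to SAE will not be considered as being dosed) in the initial dose evaluation period". Reductions are not mentioned, and the specified dose is not defined.

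The section cited is headed "6.1.3 Long-term treatment period (Week 53 to Week156"). The high-platelet rules stand in the next section, "6.1.4 Criteria for discontinuing and resuming study treatment". Section 6.1.1 refers to them correctly: the dose is fixed in Weeks 1 to 8 "except for the cases defined in the 6.1.4 Criteria for discontinuing and resuming study treatment".

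Section 6.1.4 gives two instructions that lower the dose:
- For a count above 200 x 10^9/L, "the dose of AMG531 will be reduced to the next lower dose tested".
- For a count above 400 x 10^9/L, treatment is held. Once the count is below 200, "administration of AMG531 will resume at a reduced dose by one level according to the protocol".

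The lowest arm has no level below it. If the held dose is 1 µg/kg, "treatment will be resumed at the dose of" 1 µg/kg.

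Section 12.1.1.1 evaluates the Week 9 response on the PPS and repeats the analysis on the FAS for robustness. The FAS (12.6.1) has no dose-count condition.

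**The concern.** There are two separate defects in the rule that decides who enters the primary analysis.

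First, the cross-reference cannot work. Nothing in a section on Weeks 53 to 156 can produce an interruption in Weeks 1 to 8. Read literally, a hold above 400 x 10^9/L earns no credit in any arm.

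Second, correcting the reference does not settle how reductions are counted. The protocol treats reduction and interruption as different things: 9.1.2 lists them separately among the events leading to a change of treatment, and 9.2 codes them as separate actions. A credit worded only for interruptions therefore does not obviously cover a lower dose given on schedule.

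At stake is selection on the outcome. Entry requires platelets of 30 x 10^9/L or less, so a count above 200 is a very large rise. A subject who followed the protocol exactly could be removed from the primary set because of that rise. The reduction route is closed to the 1 µg/kg arm, so losing Week 9 responders this way would lower the response rate only at 3, 6 and 10 µg/kg, in a trial meant to recommend an initial dose. The study is open-label and 12.6 fixes membership only before database lock, so an undefined term could be interpreted with responses already known.

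**Working it through.** **Inputs.** Eight weekly doses in Weeks 1 to 8 (6.1.1); a blood count before each dose (8.2.2); at least 6 qualifying doses for the PPS (12.6.2); 8 subjects per arm (3.5.1). The plan's own figure reproduces: 4 × 8 = 32. Section 12.2 says no statistical assumptions are made, so there is no power figure to check.

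**Step 1. Reduction above 200, counting only the randomised dose.** If the reduction is first applied at Week k and maintained through Week 8, the qualifying doses are k − 1.

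| First reduced dose at Week | Qualifying doses | Meets ≥ 6 |
|---|---|---|
| 2 | 1 | no |
| 3 | 2 | no |
| 4 | 3 | no |
| 5 | 4 | no |
| 6 | 5 | no |
| 7 | 6 | yes |
| 8 | 7 | yes |

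**Step 2. Hold above 400 from Week k for m weeks, then restart one level lower (3, 6 and 10 µg/kg).** With held weeks credited, the count is (k − 1) + m. For k = 3 and m = 2 it is 2 + 2 = 4, excluded. For k = 3 and m = 4 it is 2 + 4 = 6, retained. With the literal 6.1.3 reference the held weeks are not credited and the count is k − 1.

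**Step 3. Hold above 400 in any arm, continuing through Week 8.** With the literal reference the count is k − 1, so a hold starting at Week 6 or earlier excludes the subject, at 1 µg/kg too. With 6.1.4 credited it is (k − 1) + (9 − k) = 8.

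**Step 4. The other reading.** If the specified dose is whatever the protocol prescribes for that week, reduced doses qualify and nobody is excluded for a reduction.

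**Step 5. Effect on one arm.** The documents give no response rate, so these counts are assumed. Removing e Week 9 responders changes r/8 to (r − e)/(8 − e). Intervals are exact 95% (Clopper-Pearson).
- r = 4, none removed: 4/8 = 50.0% (15.7 to 84.3)
- r = 4, one removed: 3/7 = 42.9% (9.9 to 81.6)
- r = 4, two removed: 2/6 = 33.3% (4.3 to 77.7)
- r = 2, one removed: 2/8 = 25.0% becomes 1/7 = 14.3%
- r = 6, one removed: 6/8 = 75.0% becomes 5/7 = 71.4%

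**Step 6. How likely is at least one exclusion?** The trigger rate is not given either. If each of the 3 × 8 = 24 subjects at 3, 6 and 10 µg/kg independently has probability q of a reduction that leads to exclusion, the chance of at least one is 1 − (1 − q)^24. For q = 1%, 5%, 10% and 20% this is 21%, 71%, 92% and 99.5%, with 24q = 0.24, 1.2, 2.4 and 4.8 expected exclusions.

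**The case against.** The reference error is probably clerical. The wording about discontinuation criteria, together with the restriction to the initial period, fits only 6.1.4, and a sensible analyst would read it so.

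The reduction problem depends on an undefined term. Section 7 calls the starting dose the assigned dose, a different word, and 6.1.1 makes 6.1.4 changes part of planned dosing. The specified dose can therefore be read as the dose the protocol calls for that week, and then no subject is lost. Even on the narrow reading, exclusion needs a trigger by the Week 6 pre-dose count. Credited held weeks can bring the count to six, and so can the return to the held dose at counts of 50 x 10^9/L or less, which 6.1.4 allows.

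The consequence is also bounded. The primary analysis is a proportion with a confidence interval. Section 12.1.1.1 names no between-dose test and 12.2 sets no significance level. The illustrated shift is small beside intervals about 70 points wide. The FAS analysis would show any discrepancy.

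Most of this stands, and it limits the claim. It does not remove the ambiguity. The narrow reading remains plausible because 12.6.2 found it necessary to credit protocol-driven interruptions expressly and gave reductions no such credit. The FAS can reveal a difference but does not replace the PPS as primary.

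**Conclusion.** The point holds in a conditional form. Two facts are certain from the text: 12.6.2 cites the wrong section, and it does not credit reductions that 6.1.4 requires. On the narrow reading of the specified dose, a reduction first applied at Weeks 2 to 6 and maintained can exclude a fully compliant subject at 3, 6 or 10 µg/kg from the primary set. In an arm of 8 with an assumed 4 responders, one such loss costs 50.0 − 42.9 = 7.1 percentage points.

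A reader might infer that the strongest responders will drop out and that the dose comparison will be flattened. The documents do not support that: the key term is undefined, no rate of counts above 200 is given, and the count can recover. A reader might also infer that only the three higher doses are exposed. That is true of reductions, but the literal reference to 6.1.3 leaves holds above 400 uncredited in every arm, including 1 µg/kg.

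The direction of the shift assumes that the excluded subject is still a responder at Week 9. What remains is a membership rule for the primary set that can select on the outcome and is cheap to repair.

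**What to change.** In 12.6.2, and in the detailed analysis plan foreseen in 12.5:
1. Change the reference from 6.1.3 to 6.1.4.
2. Define the specified dose for the purpose of the six-dose count.
3. State that doses interrupted or reduced as 6.1.4 requires for high platelets count toward the six, and that the subject is analysed under the randomised dose.

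Settle this before set membership is decided. With it, a subject who follows the plan has 8 of 8 credited doses whatever the platelet rise, so none fails the dose-count condition for that reason.

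The cost is a sentence or two of text, with no new data, no new visits and no change to any dosing rule. The small downside is that the PPS will include some subjects who did not receive the randomised dose throughout Weeks 1 to 8; their number can be reported by arm.

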12.1.1.1 Primary endpoint

The primary endpoints will be evaluated based on the Per Protocol Set (PPS). The proportion of subjects achieving a platelet response at Week 9, and two-sided 95% confidence interval will be calculated. Platelet response is defined as 1) achieving absolute platelet increase of $\geq 20 \times 10^9/L$ above baseline or 2) increase to $\geq 10 \times 10^9/L$ and by at least 100% from baseline.

Robustness of the results will be evaluated by the analysis calculated in the same manner based on the full analysis set (FAS).

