12.6 Analysis Subsets

The analysis sets are defined below. For efficacy analysis, PPS and FAS will be used, with PPS as the primary analysis set.

Whether or not to include each subject in a particular set will be determined before database lock.

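### The primary Week 9 response rate is computed on a PPS that selects on post-randomisation dosing and SAE interruptions; the FAS should be primary

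*Combined protocol and SAP*

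**What the plan says.** All references are to the combined protocol and SAP.

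- **Primary set.** Section 12.6: "For efficacy analysis, PPS and FAS will be used, with PPS as the primary analysis set". Section 12.1.1.1 applies this to the Week 9 proportion and its two-sided 95% interval. It then plans the same calculation on the FAS as a check of robustness.
- **Membership.** Section 12.6.2 takes FAS subjects who meet the eligibility criteria, have no major protocol violation in the initial period and received the assigned dose at least six times in that period. Section 6.1.1 gives eight weekly doses. On interruptions, 12.6.2 says "dose interruption according to the dose discontinuation criteria (section 6.1.3) will be considered as" and continues "being dosed but dose interruption due to SAE will not be considered as being dosed".
- **When membership is settled.** Section 12.6: "Whether or not to include each subject in a particular set will be determined before database lock".
- **FAS.** Section 12.6.1 asks for at least one dose and a platelet count before and at least once after dosing.
- **Denominator and missing counts.** Section 12.1 takes percentages relative to the total number of subjects. Section 12.4 leaves missing counts missing, without statistical imputation.
- **Cross-reference.** Section 12.6.2 cites 6.1.3 for the discontinuation criteria. The heading there is "6.1.3 Long-term treatment period (Week 53 to Week156"). Section 6.1.1 points elsewhere: "Dose adjustment (either escalation or reduction) will not be allowed during the initial dose evaluation period except for the cases defined in the 6.1.4". Section 6.1.4 does contain the criteria.

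**The concern.** Randomisation makes the four dose arms comparable at entry. The PPS then re-selects subjects on what happened during the eight weeks in which the endpoint develops. Two features make this more than a routine per-protocol restriction.

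First, the crediting rule is asymmetric. Under 6.1.4 the stated trigger for interrupting treatment is a platelet count above 400 × 10⁹/L, so a credited interruption belongs to a subject with a large platelet rise. An uncredited interruption belongs to a subject with a serious adverse event. Retention in the primary denominator may therefore depend on both response and toxicity, and either may vary with dose.

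Second, the stated objective is to recommend an initial dose on efficacy and safety. The safety tables will still show the SAEs. The primary efficacy rate for a dose, however, would describe only subjects who received enough counted doses, and the proportion left out could differ from arm to arm.

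**Working it through.** **Inputs.** Arms of 8, four arms (3.5.1); 8 planned doses (6.1.1); at least 6 counted doses (12.6.2). The documents give no exclusion rate, expected response rate, significance level or power (12.2). Responder counts and exclusion probabilities below are assumptions.

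**Stated figure.** 4 × 8 = 32, which agrees with 3.5.1. There is no power calculation to reproduce.

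**Threshold.** 8 − 6 = 2 uncounted doses are tolerated. Two doses lost to an SAE leave 6 (kept); three leave 5 (excluded). Stopping treatment before six counted doses also excludes.

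**Effect of one exclusion from k responders among 8.**

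- Responder excluded: (k − 1)/7 − k/8 = −(8 − k)/56
- Non-responder excluded: k/7 − k/8 = +k/56

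| k/8 | Responder excluded | Non-responder excluded |
|---|---|---|
| 2/8 = 25.0% | 1/7 = 14.3% (−10.7 points) | 2/7 = 28.6% (+3.6) |
| 3/8 = 37.5% | 2/7 = 28.6% (−8.9) | 3/7 = 42.9% (+5.4) |
| 4/8 = 50.0% | 3/7 = 42.9% (−7.1) | 4/7 = 57.1% (+7.1) |
| 5/8 = 62.5% | 4/7 = 57.1% (−5.4) | 5/7 = 71.4% (+8.9) |
| 6/8 = 75.0% | 5/7 = 71.4% (−3.6) | 6/7 = 85.7% (+10.7) |

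In an arm with few responders the effect of losing a non-responder is small: zero at 0/8 and 1/56 = 1.8 points at 1/8.

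**Precision.** Clopper-Pearson 95% intervals (12.1.1.1 names no method): 5/8, 24.5 to 91.5%; 5/7, 29.0 to 96.3%; 4/7, 18.4 to 90.1%. They overlap almost fully.

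**Ordering of doses.** Two arms tied at 5/8 become 71.4% v 62.5% after one non-responder is excluded from one of them. One such exclusion cannot reverse a one-responder difference: k/7 > (k + 1)/8 needs k > 7, which is impossible among the 7 who remain. Two can: 5/6 = 83.3% exceeds 6/8 = 75.0%.

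**How likely is an exclusion?** If each subject had probability q of exclusion, the chance that an arm of 8 loses at least one is 1 − (1 − q)⁸: 33.7%, 57.0% and 83.2% for assumed q of 5%, 10% and 20%. For at least two it is 5.7%, 18.7% and 49.7%.

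**What the FAS repeat recovers.** Interrupted subjects keep their scheduled blood counts (8.2.2, 8.2.3), and early stoppers have a count one week after the last dose (8.2.5). Few treated subjects should therefore fail the post-dose rule in 12.6.1. A FAS subject with no usable Week 9 count stays in the total under 12.1 and cannot be in the numerator, so an arm with five responders and one such subject gives 5/8 = 62.5%.

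**The case against.** The strongest reply is that both rates will be produced, so the change is largely one of label. In a descriptive study with no hypothesis test (12.2) and wide intervals the label carries limited weight. It is also legitimate to ask how subjects respond when they actually receive the assigned regimen, and SAEs are tabulated by dose in everyone treated (12.1.3, 12.6.4). Much of this stands and keeps the point moderate. It does not remove it: with no test, the estimated rates are the primary result, and the plan makes the rate in the selected set the leading one. Settling membership before database lock fixes who is in the set but does not alter the selection rule.

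Three stronger readings are tempting, and the documents do not support them.

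- A reader might infer that the excluded subjects are treatment failures, so that the PPS must inflate the rate. An SAE-interrupted subject who stays on study is still measured at Week 9 and is a responder if that count qualifies. The bias is upward only if excluded subjects respond less often than those kept.
- A reader might infer that the FAS has an equally serious hole for missing Week 9 counts. On the plain reading of 12.1 such a subject already counts against the response rate. What is missing is an explicit statement. Section 6.1.2 has a no-response rule for counts unavailable because of platelet transfusion, but as a dosing rule.
- A reader might infer from the 6.1.3 citation that interruptions for high platelets in Weeks 1 to 8 are not credited. The intent is clear from 6.1.1 and 6.1.4; this is a clerical slip.

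Section 12.5 defers detail to a statistical analysis plan finalised before database lock. Denominator wording and the counting of reduced doses may be settled there. The choice of the PPS as primary is already made in Section 12.

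**Conclusion.** The point holds in a moderate form. The primary rate rests on a set defined partly by post-randomisation dosing, with SAE interruptions uncredited and criteria-driven ones credited, so exclusion may be related to dose and toxicity. One exclusion in an arm of 8 is worth −10.7 to −3.6 points (responder) or +3.6 to +10.7 points (non-responder) over assumed rates of 2/8 to 6/8. The net sign and size are unknown because the documents give neither the number excluded nor their response status. The planned FAS analysis limits the harm without changing which result is primary. The cross-reference and the silence on reduced doses are minor and would not justify a finding alone.

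**What to change.** **Main change.**

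- In 12.1.1.1, 12.6 and 12.6.2, make the FAS, analysed by randomised dose, the primary efficacy set and the PPS supportive. Nothing in the documents suggests another grouping; naming it makes it explicit. The SAE clause can stay in a supportive PPS.
- Classify SAE-interrupted subjects by their actual Week 9 count.
- State in 12.4 that a treated subject with no usable Week 9 count stays in the denominator as a non-responder, consistent with 12.1. If this is to cover a treated subject with no post-dose count at all, 12.6.1 needs the matching change.

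**Minor clean-up in 12.6.2.** Reconcile the 6.1.3 citation with 6.1.4. State how doses given at a level reduced under 6.1.4 count towards the six. If they did not count, a reduction starting at the Week w dose and not reversed would leave w − 1 full doses, so any start at or before Week 6 would exclude the subject. Section 6.1.4 allows both platelet-triggered and safety-driven reductions, so such exclusions could go either way.

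These are analysis rules only; no dosing rule is proposed. The cost is wording: no new data or visits, and both analyses are already planned. The downside is a possibly slightly less favourable primary rate.

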12.6.3 Pharmacokinetic analysis set

Pharmacokinetics will be evaluated in the subjects whose serum AMG531 concentrations are measured and who meet all of the following criteria:

- Subjects received at least one dose of AMG531; and
- Subjects whose at least one pharmacokinetic parameter is calculable.

12.6.4 Safety analysis set

Safety will be assessed in the subjects of safety analysis set who meet the following criterion:

- Subjects received at least one dose of AMG531.

13 ETHICS

13.1 Regulatory considerations

The study will be conducted in accordance with ethical principles that have their origin in the Declaration of Helsinki and are consistent with the ICH guidelines on GCP, any applicable laws and requirements, and any conditions required by a regulatory authority and/or IRB that approves this study to be conducted in its territory. Good clinical practice is defined as a standard for the design, conduct, performance, monitoring, auditing, recording, analysis, and reporting of clinical studies in a way that provides assurance that the data and reported results are credible and accurate, and that the rights, safety, and well-being of study subjects are protected.

Per GCP, the protocol will be reviewed and approved by the IRB of each participating center prior to study initiation. Serious adverse events regardless of causality will be reported to the sponsor, and the investigator will keep the IRB informed as to the progress of the study.

The investigator will explain the nature of the study and will inform the subject that participation is voluntary and that the subject can withdraw or be withdrawn from the study at any time. Written informed consent will be obtained from each subject prior to the screening procedures to determine if study eligibility criteria are met. A copy of the

signed consent form will be given to every subject, and the original will be maintained with the subject's records.

13.2 Institutional Review Board

A list of IRB members or a Statement of GCP Compliance should be obtained by the investigator and provided to the sponsor.

Any documents that the IRB may need to fulfill its responsibilities, such as protocol amendments, and information concerning subject recruitment, payment, or compensation procedures, or information from the sponsor will be submitted to the IRB. The IRB's written unconditional approval of the study protocol, the informed consent form(s), and any other written materials to be provided to subjects will be in the possession of the investigator and the sponsor before the study is initiated. The IRB's unconditional approval statement will be transmitted by the investigator to the sponsor prior to shipment of investigational product supplies to the investigative site. This approval must refer to the study by exact protocol title and number, and should identify the documents reviewed and the date of review.

Protocol modifications or changes may not be initiated without prior written IRB approval except when necessary to eliminate immediate hazards to the subjects or when the change(s) involves only logistical or administrative aspects of the study. Such modifications will be submitted to the IRB and written verification that the modification was submitted should be obtained.

The IRB must be informed by the investigator of informed consent form changes or revisions of other documents originally submitted for review; serious and/or unexpected adverse experiences occurring during the study; new information that may affect adversely the safety of the subjects or the conduct of the study; an annual update and/or request for reapproval; and when the study has been completed.

